9.4 Statistical analysis

Descriptive statistics and univariate and multivariate analysis will be used to characterize the study population. The endpoint of analysis of treatment toxicity will be done primarily by tabulation of the incidence of side effects with CTCAE grade 2 or more (see Appendix B) or acute GvHD overall grade III or more (see Appendix C). Actuarial competing risk estimates of probability of death will be split by cause of death where a difference will be made between death due to CMV disease and death due to side effects of the treatment. The endpoints of presence of CMV-specific T cells and number of complete remissions and partial remissions of CMV reactivation or CMV disease after administration of CMV pp65-specific T cells will be documented.

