7. METHODS

7.1 Study endpoints

- The number of events of acute GvHD, death and all other adverse events.
- The number of CMV-specific T cells at different time points after infusion of CMV pp65-specific T cells.
- The number of complete responses or partial responses of CMV reactivation or CMV disease after infusion of CMV pp65-specific T cells.

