7.3 Evaluation criteria

7.3.1 Safety evaluation after treatment

General non GvHD toxicity will be scored according to the NCI Common Terminology Criteria for Adverse Events (CTCAE) Version 4.0 (see appendix B) In case of grade 3 or 4 toxicity after infusion of CMV pp65-specific T cells, further administrations of CMV pp65-specific T cells will be cancelled in that patient.

Acute GvHD will be graded using the criteria outlined in appendix C. In case of grade 3 or 4 acute overall GvHD after infusion of CMV pp65-specific T cells, further administrations of CMV pp65-specific T cells will be cancelled in that patient.

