8.2 Adverse and serious adverse events

Adverse events are defined as any undesirable experience occurring to a subject during a clinical trial, whether or not considered related to the investigational drug. All adverse events reported spontaneously by the subject or observed by the investigator will be recorded.

A serious adverse event (SAE) is any untoward medical occurrence or effect that at any dose results:

- in death;
- is life threatening (at the time of the event);
- requires hospitalization or prolongation of existing inpatients' hospitalization;
- in persistent or significant disability or incapacity.

All SAEs will be reported through the web portal *ToetsingOnline* to the CCMO, within 15 days after the sponsor has first knowledge of the serious adverse reactions. SAEs that result in death or are life threatening should be reported expedited. The expedited reporting will occur not later than 7 days after the responsible investigator has first knowledge of the adverse reaction. This is for a preliminary report with another 8 days for completion of the report.

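### The primary toxicity table in 9.4 covers only part of the safety endpoint declared in 7.1, and its term for non-GvHD events is undefined

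*Protocol*

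**What the plan says.** Protocol 7.1 lists as its first endpoint "The number of events of acute GvHD, death and all other adverse events", with no limit by grade or cause. Section 8.2 defines an adverse event as one that counts "whether or not considered related to the investigational drug", and adds: "All adverse events reported spontaneously by the subject or observed by the investigator will be recorded". Section 7.3.1 states: "General non GvHD toxicity will be scored according to the NCI Common Terminology Criteria for Adverse Events (CTCAE) Version 4.0". Acute GvHD is graded separately by Appendix C.

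The analysis is in 9.4: "The endpoint of analysis of treatment toxicity will be done primarily by tabulation". In full, this is "tabulation of the incidence of side effects with CTCAE grade 2 or more", or acute GvHD of overall grade III or more. Deaths are handled apart, by competing-risk estimates that distinguish "death due to CMV disease and death due to side effects of the treatment".

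Section 7.5 closes inclusion temporarily if the overall grade of acute GvHD rises by more than one point in 2 of the first 3, 3 of the first 6 or 4 of the first 10 patients. Sections 3 and 9.1 describe an open-label, non-randomized study. It has no control arm.

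**The concern.** Safety and tolerability belong to the first objective (section 2). The endpoint that serves it is broad, but the one table to which 9.4 commits is narrower in two ways that are plain from the text, and perhaps in a third.

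- Grade 1 adverse events are left out.
- Acute GvHD of grade I and II is left out. GvHD is the one risk named in 10.3.
- If 'side effects' means events blamed on the cells, events that the investigator ascribes to something else are left out too. Other explanations are always at hand in these patients: CMV disease, the transplant itself, and antivirals, which continue after infusion (5.5) and which section 1 links to myelosuppression and nephrotoxicity.

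With no control arm, this table is much of what a reader will use to judge the product. A table narrower than the endpoint can equal the declared count or fall below it. It cannot exceed it.

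**Working it through.** The plan gives no figure for safety. Its one computed figure, 15 patients, concerns response and enters below only as the denominator.

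**Step 1. Endpoint and primary table side by side.**

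| Component | Endpoint (7.1, 8.2) | Primary table (9.4) | Outside the table |
|---|---|---|---|
| Non-GvHD events, grade | any | CTCAE 2 or more | grade 1 |
| Non-GvHD events, cause | any | 'side effects', undefined | unattributed events, if the term means related |
| Acute GvHD | all | overall grade III or more | grades I and II |
| Death | all | separate competing-risk estimates | none, though the split by cause needs judgement |

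**Step 2. GvHD table against pause rule.** Assume that the rise in 7.5 is measured from the grade at infusion and that no GvHD is grade 0. Section 5.4 rules out infusion at grade III or higher, so the starting grade is 0, I or II. The rises of more than one point are then 0 to II, 0 to III, 0 to IV, I to III, I to IV and II to IV. Five of the six end at grade III or IV and enter the table. The sixth, 0 to II, does not.

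If every qualifying rise were of that kind, the rule would be met at 2/3, 3/6 or 4/10 = 40% while the GvHD part of the primary table read 0/3, 0/6 or 0/10. This is a logical limit, not a forecast.

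**Step 3. What 'side effects' means.** No section defines it.

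Pointing to treatment-related events:
- 9.4 calls its subject treatment toxicity, and its next sentence sets side effects of the treatment against CMV disease.
- Sections 1 and 6.3 report no side effects in six patients treated under the earlier protocol. For transplant recipients with refractory CMV, that is hard to read as no adverse event of any cause.
- Where events of any cause are meant, 7.1, 8.2, 8.3 and 9.3 say adverse events.

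Pointing to loose wording for adverse events:
- The phrase is tied to CTCAE grading through Appendix B, which sets no condition of relatedness.
- 7.3.1 speaks of toxicity after infusion, which is a condition of time.
- No section provides a step for attributing non-serious events.

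The first reading is the more natural. The text does not settle it.

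**Step 4. Size if the first reading is right.** The documents give no adverse event rate and no share attributed, so both are assumed. Suppose 10 of 15 patients have an event of grade 2 or more, and x of them have it attributed to the product. The exact 95% limits are the 0.025 quantile of Beta(x, 16 − x) and the 0.975 quantile of Beta(x + 1, 15 − x). For x = 0 the lower limit is 0.

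| Patients in table | Rate | 95% interval |
|---|---|---|
| 10/15 (all causes) | 66.7% | 38.4 to 88.2% |
| 5/15 | 33.3% | 11.8 to 61.6% |
| 2/15 | 13.3% | 1.7 to 40.5% |
| 1/15 | 6.7% | 0.2 to 31.9% |
| 0/15 | 0% | 0 to 21.8% |

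If instead 6, 9 or 12 of 15 had such an event, the all-cause rate would be 40%, 60% or 80%. The filtered table could read anything from 0% up to that figure.

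**The case against.** The strongest reply is that the plan loses nothing. All adverse events are recorded and followed (8.2, 8.3), toxicity is graded, all SAEs go to the ethics authority, and the annual report contains a complete safety analysis (8.2.2). A grade threshold in a primary display is a choice of presentation, and full listings are commonly left to a statistical analysis plan, which may exist. In so ill a population an all-cause table is also full of background events that no control arm can subtract, so attributed events carry information.

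Much of this stands, and it limits the point. A reader might infer that 9.4 reports nothing but these events. It does not say so: the word is 'primarily', which leaves room for further tables, and deaths are estimated separately. A reader might also infer that the trial's safety result rests on unblinded attribution. The documents do not support that. The GvHD tabulation, the pause rule in 7.5, the cancellation of further infusions after toxicity (7.3.1) and SAE reporting carry no stated condition of relatedness. Only the non-GvHD table and the cause-of-death split could depend on attribution, and for the table this rests on one reading of an undefined word.

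What the reply does not remove is the mismatch. 'Primarily' permits a table of all adverse events but commits to none, and the GvHD gap needs no guess about wording. The value of attributed events is a reason to show them in a column, not to filter by them.

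**Conclusion.** The point holds as a mismatch between the declared safety endpoint and the primary analysis of it. Two parts are certain from the text: grade 1 events and acute GvHD of grade I and II are outside the primary table, and a 0 to II rise counts in 7.5 but not in that table. The possible gap on GvHD runs up to 4/10 against 0/10, assuming that the rise is measured from the grade at infusion.

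A third part is conditional. If 'side effects' means treatment-related events, the non-GvHD table depends on open-label judgement with no stated criteria and could understate harm. Its size cannot be derived from the documents, and the figures in step 4 only show the possible span.

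No sample size, error rate or stopping rule changes. The sentence should be amended, but this is a reporting fault and not a flaw in the design.

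**What to change.** In 9.4, replace the present tabulation by one of adverse events as defined in 8.2, regardless of attribution, and of all acute GvHD, each by worst grade per patient from first infusion to end of follow-up. Keep CTCAE grade 2 or more and acute GvHD grade III or more as summary lines. Show events that the investigator attributes to the product as an additional column rather than as the filter. Giving the GvHD grade at infusion beside the worst grade would let a reader match the table to 7.5.

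The cost is one rewritten sentence, a longer table and less favourable headline figures. No new data are needed for the all-cause table, because 8.2 already records every adverse event and 7.5 already requires the change in GvHD grade.

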2. OBJECTIVES

- To assess the feasibility, tolerability and safety of administration of donor derived CMV pp65-specific T cells in patients with CMV reactivation or CMV disease after alloSCT.
- To determine the presence of CMV-specific T cells at different time points after infusion of CMV pp65-specific T cells.
- To evaluate whether administration of CMV pp65-specific T cells in patients with persistent CMV reactivation or CMV disease after alloSCT leads to complete or partial responses.

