9.3 Power calculation

We consider the infusion of CMV pp65-specific T cells a success when the response rate is at least 66 % (p_1 ; 2/3 of patients). Based on our historical experience, we estimate the rate of responses with pharmacotherapy alone but without immune intervention to be 30% ($=p_0$) for the targeted patient population. Given the high laboratory effort and associated costs of treatment with CMV pp65-specific T cells, the trial should have a power of 90% (beta-error 0.1). With the usual alfa-error of 0.05, the sample size as calculated according to the standard Fleming design is 15 treated patients under these assumptions. We expect no excess in number of events of acute GvHD, death and all other adverse events.

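### No endpoint is named primary, the powered response endpoint is only documented in 9.4, and the 66% success sentence does not match the rule that gives N=15

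*Protocol*

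**What the plan says.** The objectives in section 2 and the endpoints in 7.1 are lists of three items without ranking. The first objective is "To assess the feasibility, tolerability and safety of administration of donor derived CMV pp65-specific T cells" and the first endpoint is "The number of events of acute GvHD, death and all other adverse events". Complete or partial response comes third in both lists. The word primary is attached to none of them.

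Sections 4.4 and 9.3 base the sample size on response only. They take 30% as the rate with pharmacotherapy alone (p0) and 66%, also written as 2/3, as p1. Power is 90%, and the error rate is introduced with "With the usual alfa-error of 0.05"; no sidedness is given. A Fleming design then yields 15 treated patients. The same paragraph states: "We consider the infusion of CMV pp65-specific T cells a success when the response rate is at least 66" per cent.

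Section 9.4 says of toxicity: "The endpoint of analysis of treatment toxicity will be done primarily by tabulation of the incidence of side effects". Of response it says only that the "number of complete remissions and partial remissions of CMV reactivation or CMV disease after administration of CMV pp65-specific T cells will be documented".

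**The concern.** One endpoint carries the error rates and the success statement, but it is not designated primary, and the protocol's own analysis section gives it no comparison. Carried out as written, 9.4 produces a count of responders. It never makes the comparison with 30% that fixed N at 15.

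The success sentence in 9.3 does not fill the gap. It attaches success to 66%, which is the alternative used for power, not the boundary of the test. If the team judges the observed rate against 66%, the trial runs under a much stricter rule than the one it was sized for. If it uses the Fleming cut-off, it uses a rule that is nowhere written down. In an open-label single-arm study, that choice could be made after the responses are known.

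**Working it through.** **Inputs, all from 9.3 (repeated in 4.4):** p0 = 0.30, p1 = 0.66 (or 2/3), alpha = 0.05, power = 0.90, N = 15.

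**1. Reproduce N.** One-stage Fleming approximation:

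n = [(z(1−alpha)·√(p0·q0) + z(1−beta)·√(p1·q1)) / (p1 − p0)]², with q = 1 − p

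- One-sided 0.05, p1 = 0.66: [(1.645·√0.21 + 1.282·√0.2244) / 0.36]² = 14.29, so **15**. This matches the plan.
- One-sided 0.05, p1 = 2/3: 13.71, so 14.
- Two-sided 0.05: 17.48, so 18, at 0.66; 16.79, so 17, at 2/3.

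The stated N therefore corresponds to a one-sided 0.05 test with p1 = 0.66.

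**2. Cut-off implied by that design.** 15·0.30 + 1.645·√(15·0.30·0.70) = 4.5 + 2.92 = 7.42, so reject 30% at **8 or more of 15**.

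**3. Cut-off implied by the success sentence, read as an observed rate.** 9/15 = 60% falls short of 66%; 10/15 = 66.7% reaches it. The rule is **10 or more of 15**.

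**4. Exact binomial properties with n = 15.** Alpha is P(X ≥ r) at 0.30; power is P(X ≥ r) at p1.

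| Rule | Alpha | Power at 0.66 | Power at 2/3 |
|---|---|---|---|
| ≥8 (Fleming) | 0.05001 | 0.902 | 0.912 |
| ≥9 | 0.0152 | 0.781 | 0.797 |
| ≥10 (66% observed) | 0.0037 | 0.597 | 0.618 |

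**5. How often the two rules disagree.** They differ when 8 or 9 patients respond. At a true rate of 0.66 that probability is 0.902 − 0.597 = 0.305, or **31%**. At 2/3 it is 29%, and at 0.60 it is 38%.

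**6. A point that the fix must respect.** P(X ≥ 8) at 0.30 is 0.05001, just above 0.05, and the exact 90% lower limit at 8/15 is 0.29999, just below 0.30. A strict exact test at 0.05 would therefore need 9 of 15, and power would be 0.781. Keeping exact alpha at or below 0.05 with 90% power needs n = 17 with 9 or more responders (alpha 0.040, power 0.916).

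**The case against.** The strongest reply is that a Fleming design is itself a testing procedure. Given p0, p1, alpha and power, the cut-off of 8 follows, and response is the only endpoint it could apply to. 9.3 labels 66% as p1, so a statistician would recognise it as the alternative. The wording of tests and intervals commonly sits in a statistical analysis plan, which is not at hand.

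Much of this is fair: the cut-off can be derived, as shown above, and the lack of test detail alone would not be a finding. Two things remain. Which endpoint is primary is a matter for the protocol. And the protocol does speak on both points: it ties success to 66%, and it says that response will be documented. A later plan that tested at 8 of 15 would depart from the plain reading of both sentences.

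Three stronger readings are tempting and are not supported:

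- A reader might infer that 9.4 makes toxicity the primary endpoint. The adverb there describes how toxicity is analysed, by tabulation. It does not rank toxicity above response.
- A reader might infer that response and safety can give opposite verdicts. Safety has no pass or fail criterion at the end of the study. The acute GvHD counts in 7.5 trigger a temporary closure and a discussion of benefit against harm.
- A reader might take response to mean complete response alone, since 6.3 reports clearance in the preceding study. Section 2 and 7.1 both say complete or partial, and 6.3 describes another protocol with a different product. This reading is weak, though 9.3 would be clearer if it defined its term.

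**Conclusion.** The point holds as a defect in how the powered endpoint is fixed. No endpoint is designated primary, the response comparison that set N = 15 does not appear in 9.4, and the one written success criterion does not describe the rule behind the sample size. Applied literally to the observed rate, that criterion has power of about 0.60 instead of the stated 0.90, with alpha 0.004. The two rules reach different conclusions in 31% of trials if the true rate is 66%.

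These figures assume 15 evaluable treated patients, independent responses, a one-sided test (the protocol does not say, but only this reproduces 15), and that the 66% sentence refers to the observed rate. If it refers to the true rate, the power loss disappears, but the protocol then states no success rule for the data at all.

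The sample size itself is sound under the Fleming approximation. The change is worth making before response data are seen, but it does not call the design into question.

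**What to change.** - **7.1 and 9.4:** name the proportion of treated patients with complete or partial response, as defined in 7.3.2, as the primary efficacy endpoint.
- **9.4:** for this endpoint, replace the statement that it is documented with the one-sided Fleming comparison against 30%. State the rule as 8 or more responders of 15 (exact alpha 0.05001, power 0.90 at 66%) and report the exact 90% interval. Write the rule as a count: a condition of exact p ≤ 0.05 would move the cut to 9 and lower power to 0.781.
- **9.3 and 4.4:** present 66% as the design alternative p1, not as the observed rate required for success, say that the test is one-sided, and define response rate as complete plus partial response.
- **9.4:** label complete response alone and CMV-specific T-cell counts as secondary and descriptive. Report acute GvHD and death over all 15 patients with exact intervals beside the response result, stating the GvHD definition used, since 9.4 tabulates overall grade III or more while 7.5 counts an increase in grade.

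The cost is wording only, with no added patients, visits or data. The sponsor gives up the freedom to choose the headline afterwards and accepts an exact alpha marginally above 0.05. If strict exact control is wanted, the price is two more patients (n = 17, 9 or more responders). The safety intervals will be wide: 0 events in 15 still has a two-sided 95% upper limit of 1 − 0.025^(1/15) = 21.8%.

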9.5 Interim analysis

After the first 3, 6 and 10 patients an interim analysis will be performed by the principal investigator.

10. ETHICAL CONSIDERATION

10.1 Regulation statement

The study will be conducted according to the principles of the Declaration of Helsinki (version 2008) and in accordance with the Medical Research Involving Human Subjects Act (WMO).

10.2 Recruitment and consent

The treating physician will inform the patient (and in case of a minor their parents or guardians) about this study and explain the patient (and in case of a minor their parents or guardians) about the informed consent procedure. All patients (and in the case of a minor their parents or guardians) will be informed of the aims of the study, the possible adverse events, the procedures and possible hazards to which the patient will be exposed. They will be informed as to the strict confidentiality of their patient data, but that their medical records may be reviewed for trial purposes by authorized individuals other than their treating physician. It will be emphasized that the participation is voluntary and that the patient (and in case of a minor their parents or guardians) is allowed to refuse further participation in the protocol whenever he/she wants. This will not prejudice the patient's subsequent care. The patient (and in case of a minor their parents or guardians) is given the information letter. During a second visit, information will be repeated if necessary and participation to the study will be considered.

For children below the age of 12 years written informed consent will be obtained from both parents or guardians. Children aged between 12-17 years of age must give their written informed consent, unless these children are not capable to give their consent, together with both parents or guardians. Only after written informed consent is obtained will the participants be entered into the study.

10.3 Benefits and risks assessment

Potential benefit of participation to this study is a reduction of the CMV DNA load which may lead to a reduction of development of severe CMV disease or cure of CMV disease. A potential risk of participation to this study is development of acute GvHD.

10.4 Compensation for injury

The chance of injury as a result of this study is extremely small. However, the LUMC has insured this risk by taking a liability insurance, which is in accordance with article 7, subsection 6 of the WMO.

The LUMC (also) has an insurance which is in accordance with the legal requirements in the Netherlands (Article 7 WMO and the Measure regarding Compulsory Insurance for Clinical Research in Humans of 23th June 2003).

This insurance provides cover for damage to research subjects through injury or death caused by the study.

1. € 450.000,-- (i.e. four hundred and fifty thousand Euro) for death or injury for each subject who participates in the Research;
2. € 3.500.000,-- (i.e. three million five hundred thousand Euro) for death or injury for all subjects who participate in the Research;
3. € 5.000.000,-- (i.e. five million Euro) for the total damage incurred by the organization for all damage disclosed by scientific research for the Sponsor as 'verrichter' in the meaning of said Act in each year of insurance coverage.

The insurance applies to the damage that becomes apparent during the study or within 4 years after the end of the study.

